### 2.5.3 Handling of intercurrent events

The primary analysis will include data from participants regardless whether early termination from the study, interruption of study treatment, or intensified concomitant treatment (local and systemic) has occurred.

### 2.5.4 Handling of missing values not related to intercurrent event

#### Missing baseline value

If the baseline ESSDAI total score is missing, the screening value (if available) will be used to impute the baseline value. If neither the ESSDAI total score at baseline nor the ESSDAI total score at screening can be calculated due to missing domain scores, then the baseline ESSDAI total score is calculated using combination of baseline visit domain scores (where those are not missing) and screening domain scores (where the baseline analogs are missing) if they are available, and otherwise the baseline ESSDAI total score is set to missing.

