5.1 Inclusion criteria

Subjects eligible for inclusion in this study have to fulfill all of the following criteria at the time of screening evaluations unless otherwise noted.

1. Signed informed consent must be obtained before any study assessment is performed.
2. Male or female patients aged 18 to 75 years
3. Classification of Sjögren's Syndrome according to the 2016 ACR/EULAR criteria ([Shiboski et al 2017](#)).
4. Screening ESSDAI (based on weighted score) ≥ 5 derived from 8 domains (biologic, hematologic, articular, cutaneous, glandular, lymphadenopathy, renal, constitutional). Subjects with involvement of one or more of the remaining 4 domains are eligible but scores of these domains will not contribute to the assessment for eligibility, but will be part of the overall ESSDAI for that subject.
5. Screening ESSPRI ≥ 5
6. Seropositive for anti-Ro/SSA antibodies at or within 3 months prior to screening
7. Unstimulated whole salivary flow rate of > 0 mL/min.
8. Able to communicate well with the Investigator to understand and comply with the requirements of the study.

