8.3.1 EULAR Sjögren's Syndrome Disease Activity Index (ESSDAI)

ESSDAI ([Section 16.4](#)) is a validated disease outcome measure for Sjögren's Syndrome that will be applied to the study subjects. The instrument contains 12 organ-specific domains contributing to disease activity. For each domain, features of disease activity are scored in 3 or 4 levels according to their severity. These scores are then summed across the 12 domains in a weighted manner to provide the total score. The domains (weights) are as follows: constitutional (3), lymphadenopathy (4), glandular (2), articular (2), cutaneous (3), pulmonary (5), renal (5), muscular (6), PNS (5), CNS (5), hematological (2), and biological (1). The maximum possible score is 123.

To calculate ESSDAI, all 12 organ domains must be individually assessed at every scheduled timepoint (from screening visit till end of study). Domain assessments will be entered into a tablet (provided by a central vendor) and ESSDAI score will be calculated by the software. At screening, the ESSDAI subscore from 8 pre-selected domains listed in the inclusion criterion #7, will be calculated to determine patient's eligibility.

For assessments not listed in the protocol as mandatory tests but which may be needed to estimate ESSDAI, including radiography, high resolution computer tomography (HRCT), lung function test (DLCO, FVC), estimated glomerular filtration rate (eGFR), electromyography (EMG), muscle (or any other) biopsy, it is at the investigator's discretion to have these assessed based on the signs and symptoms of the patient so to provide correct ESSDAI readout.

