#### 2.1.1 General definitions

The term '*study treatment*' or '*study drug*' refers to the Novartis investigational drug, LOU064 or placebo, dispensed by the investigators during the study. Specifically, the following grouping scheme will be used for reporting of summaries:

Placebo

LOU064 100 mg *qd*

LOU064 100 mg *bid*

Any LOU064 (i.e. LOU064 100 mg *qd* and 100 mg *bid* combined)

The term '*date of first administration of study drug/treatment*' refers to the date on which the study drug/treatment was given for the first time in the CLOU064E12201 study.

The term '*date of last administration of study drug/treatment*' refers to the date on which the study drug/treatment was given for the last time in the CLOU064E12201 study.

The term '*study day*' refers to the Analysis Relative Day, Relative Start Day or Relative End Day, as applicable. Day 1 is defined as the date of first dose of study drug (LOU064 or placebo). Study day is defined as the number of days since the date of first dose of study treatment (Day 1).

Therefore, for a particular date, study day will be calculated as follows:

- for dates on or after the first administration of study treatment,  
Study day = Assessment date – Date of first dose of study treatment +1
- for dates prior to the date of first administration of study treatment,  
Study day = Assessment date – Date of first dose of study treatment.

The term '**baseline**' refers to the last assessment performed prior to administration of the first dose of study treatment. In case the scheduled baseline assessment value is missing, the screening value if available will be used instead.

The term '**treatment-emergent adverse event**' refers to any adverse event (AE) started after the first dose of study treatment, or events present prior to the first dose of study treatment but increased in severity (based on preferred term (PT)).

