#### **2.5.1 Primary endpoint**

The ESSDAI score is obtained by summation of the twelve domain scores. Each domain score is obtained by multiplying the activity level with the domain weight. The maximum theoretical ESSDAI score is 123. For details on ESSDAI calculation, please refer to Appendix 5.5.1.

The ESSDAI score will be listed by treatment group, subject and visit/time. Descriptive statistics will be provided by treatment group and visit/time on both raw and change from baseline values.

Spaghetti plots of ESSDAI up to Week 24 will be provided by treatment over time.

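### For a partly scored Day 1 ESSDAI, the missing-baseline rule substitutes the whole screening total when filling only the missing domains would be more accurate (minor)

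*SAP*

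**What the plan says.** SAP 2.5.4 (under Missing baseline value) and protocol 12.4.3 give the same rule in the same order.

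- Step 1: "If the baseline ESSDAI total score is missing, the screening value (if available) will be used to impute the baseline value".
- Step 2 has a condition: "If neither the ESSDAI total score at baseline nor the ESSDAI total score at screening can be calculated due to missing domain scores". Only then is it the case that "the baseline ESSDAI total score is calculated using combination of baseline visit domain scores" where those exist, with screening domains filling the gaps.
- If that also fails, the baseline is missing.

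SAP 2.1.1 defines baseline as the last assessment before the first dose and adds the general rule "In case the scheduled baseline assessment value is missing, the screening value if available will be used instead".

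Other relevant text:

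- Protocol 8.3.1: "The instrument contains 12 organ-specific domains contributing to disease activity".
- Protocol section 3: screening lasts up to 6 weeks.
- Protocol 5.1: entry requires "Screening ESSDAI (based on weighted score) ≥ 5 derived from 8 domains".
- SAP 2.5.2: baseline ESSDAI is subtracted to form each change score and is a continuous covariate in the MMRM.
- SAP 2.1: the <10/≥10 stratum is taken from the database, not from IRT, so an imputed baseline can change it.

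**The concern.** The order of the two steps is hard to defend. Take two patients who each lack one Day 1 domain. The one with a complete screening score has all 11 observed Day 1 domains replaced. The one whose screening score is also incomplete keeps them. Better screening data thus give a less accurate baseline. The more accurate rule is already in the plan but is reached only as a last resort.

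The substituted total is older, and it is the score on which eligibility was judged, so regression to the mean makes it likely to lie somewhat above the Day 1 value. For an affected patient the error enters the covariate, possibly the stratum, and every unadjusted change from baseline. The stratum is also the subgroup of interest in SAP 2.2.1.

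**Working it through.** **1. The plan's own figure.** Weight × highest level over the 12 domains of protocol Table 16-5, in table order: 6+12+4+6+9+15+15+18+15+15+6+2 = 123. This matches SAP 2.5.1 ("The maximum theoretical ESSDAI score is 123"). Effect size, SD and power are redacted, so no sample-size figure can be reproduced.

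**2. Error ratio for one affected patient.** Let d_j be the weighted screening score minus the weighted Day 1 score in domain j.

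- Whole substitution: error Σd_j. If the d_j are uncorrelated with mean near zero, the mean square is Σσ_j².
- Filling one domain, each equally likely to be missing: mean square (1/12)Σσ_j².
- RMSE ratio: √12 = 3.46. With k domains missing it is √(12/k): 2.0 for k = 3, 1.4 for k = 6, 1 for k = 12.

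This ratio does not depend on how variable ESSDAI is; the absolute errors do. One bound comes directly from the documents. If only the biological domain is missing (weight 1, levels 0-2), filling it can be wrong by at most 2 points, whereas whole substitution is exposed to change in all 12 domains.

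**3. Illustrative absolute size.** Simulated independent ordinal domains with the protocol weights, entry if the 8-domain screening score is ≥5, and one random domain missing on Day 1. The following are assumptions, not in the documents:

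- Share of patients with any activity, before selection: constitutional 25%, lymphadenopathy 15%, glandular 30%, articular 60%, cutaneous 15%, pulmonary 10%, renal 5%, muscular 3%, PNS 8%, CNS 1%, haematological 35%, biological 55%.
- Latent screening-to-Day-1 correlation 0.60 to 0.95.

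| Latent correlation | Whole total: bias / RMSE / wrong stratum | One domain filled: bias / RMSE / wrong stratum | RMSE ratio |
|---|---|---|---|
| 0.60 | +1.27 / 7.27 / 39.1% | +0.11 / 2.15 / 5.6% | 3.38 |
| 0.70 | +1.03 / 6.66 / 35.7% | +0.09 / 1.97 / 5.0% | 3.38 |
| 0.80 | +0.81 / 5.87 / 31.3% | +0.07 / 1.74 / 4.2% | 3.37 |
| 0.90 | +0.52 / 4.71 / 24.7% | +0.04 / 1.37 / 3.0% | 3.44 |
| 0.95 | +0.33 / 3.79 / 19.3% | +0.03 / 1.10 / 2.2% | 3.45 |

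Other assumed prevalences (three sets, correlation 0.80-0.99) gave RMSE 1.7-7.2, bias +0.1 to +0.9 and wrong stratum 8-30% for whole substitution.

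**4. Effect on the treatment comparison.** Write the model as Y − b = α + τT + βb. Then Y = α + τT + (1+β)b, with the same τ. Subtracting a wrong baseline therefore does not itself reach the contrast; the error acts only through the covariate and stratum. It arises before the first dose and under blinding, so its expectation is the same in every arm.

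A check used 4,000 simulated trials of 24/24/24 (72/3 = 24, SAP 1.1). Each was analysed by ANCOVA at Week 24 on baseline and stratum, pooled LOU064 against placebo. Further assumptions were a true difference of −2 points and a latent Day-1-to-Week-24 correlation of 0.8. Each cell gives latent correlation 0.7 / 0.9.

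| Patients affected | SE, true Day 1 baseline | SE, plan's rule | Inflation | SE, domain filled | Shift in unadjusted placebo change |
|---|---|---|---|---|---|
| 2% | 1.327 / 1.320 | 1.331 / 1.324 | 0.3% / 0.3% | 1.328 / 1.320 | −0.02 / −0.01 |
| 5% | 1.299 / 1.325 | 1.316 / 1.330 | 1.3% / 0.4% | 1.299 / 1.324 | −0.05 / −0.02 |
| 10% | 1.310 / 1.335 | 1.332 / 1.339 | 1.7% / 0.3% | 1.312 / 1.335 | −0.10 / −0.05 |
| 25% | 1.328 / 1.352 | 1.399 / 1.391 | 5.3% / 2.9% | 1.337 / 1.357 | −0.28 / −0.14 |

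In every row the mean LOU064-placebo difference under the plan's rule stayed within 0.02 points of that with the true Day 1 baseline (largest gap 0.014).

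**5. In patients.** An inflation of 1.7% is equivalent to losing 72 × (1 − 1/1.017²) ≈ 2.4 patients; 0.3% is about 0.4. If 5% are affected (3.6 patients), whole substitution puts 3.6 × 0.193 to 3.6 × 0.391 ≈ 0.7 to 1.4 patients in the wrong stratum, against 0.1 to 0.2 with domain filling.

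**The case against.** Several points on the other side stand.

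- **Partial baselines should be rare.** Protocol 8.3.1 requires that "all 12 organ domains must be individually assessed at every scheduled timepoint (from screening visit till end of study"), with tablet entry and the score calculated by software. Protocol section 3 requires baseline assessments to be complete before Day 1 dosing. If no Day 1 domain was scored, both orders give the same value.
- **The ratio of 3.5 is arithmetic.** It follows from comparing twelve domain errors with one and is not evidence about this trial. The absolute figures are one slice of a wide range.
- **One step is inferred.** The explicit rule that one missing domain makes the total missing is written for post-dose visits. At baseline it is implied by the wording about totals that cannot be calculated because domain scores are missing. Appendix 5.5.1, on calculating ESSDAI, is redacted, and so are the supplementary analyses.
- **The stratum source is already settled.** SAP 2.1 uses the database value, so that part needs no change. A wrong stratum is also softened by having continuous baseline ESSDAI in the same model.
- **The fix has a cost.** It produces a total from two dates, departs from the general rule in SAP 2.1.1, and touches protocol text that protocol 14.1 allows to be changed only by a written amendment.

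These points limit the size of the problem but do not justify the order. A total that mixes 11 Day 1 domains with one older domain is still closer to Day 1 than one in which all twelve are older.

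**Conclusion.** The point holds as a minor one. For a patient with a partly scored Day 1 ESSDAI and a complete screening score, the rule discards up to 11 observed domain scores. With one domain missing, this gives a baseline error about 3.5 times larger than necessary. That ratio rests on roughly independent domain changes; the absolute errors rest on assumed prevalences and visit-to-visit correlation. The upward direction is likely, because patients were selected on the screening score.

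A reader might infer that an inflated baseline biases the primary comparison or exaggerates the LOU064 effect. The documents do not support this: the error is unrelated to arm, and baseline is a covariate. What remains is a small loss of precision (0.3% on the standard error at 2% affected, 0.3-1.7% at 5-10%), some wrong strata, and unadjusted within-arm changes shifted slightly towards improvement. The true rate of partial baselines is not given and is probably low.

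**What to change.** Before unblinding, reorder the rule in SAP 2.5.4:

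1. State that the Day 1 total is incalculable if any domain is missing. Keep every observed Day 1 domain and fill each missing one from the same domain at screening.
2. Use the whole screening total only if no Day 1 domain was scored.
3. If a domain is missing at both visits, the baseline stays missing, as now.

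Align SAP 2.1.1 for ESSDAI. Record the change in SAP section 4, which now states that there are none, and in protocol 12.4.3 at the next amendment. Report the number of imputed baselines per arm, separating partly filled scores from whole substitutions.

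The cost is a few lines of derivation code and the documentation of the change; no new data are needed.

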#### Other missing data

For post-dose time points with missing data in one of the domains of the ESSDAI, the ESSDAI total score will be set to missing.

The MMRM utilized for the primary analysis implicitly imputes missing data under a missing at random assumption.

### 2.5.5 Sensitivity analyses

N/A.

## 2.5.6 Supplementary analyses

Commercially Confidential Information

## 2.6 Analysis supporting secondary objectives

The FAS analysis set will be used for the analysis described here.

### 2.6.1 Secondary endpoint(s)

Secondary endpoints of interest are the following:

- ESSPRI
  - The total score of ESSPRI is defined as the mean of the three domains (pain, fatigue and dryness). If at least one of the domains is missing, then the total score of ESSPRI will not be derived for the corresponding subject.
- FACIT-F
  - The total score of FACIT-F will be used to assess the impact on fatigue. The FACIT-F contains 13 questions, where each has a scale from 0 to 4, where 0 is for “Not at all”, 1 is for “A little bit”, 2 is for “Somewhat”, 3 is for “Quite a bit” and 4 is for “Very much”. For details on total score of FACIT-F calculation, please refer to Appendix 5.5.2.
- EQ-5D
  - The EQ-5D consists of a descriptive system and the EQ VAS scale.

The descriptive system comprises five dimensions: mobility, self-care, usual activities, pain/discomfort and anxiety/depression. This can be used as a quantitative measure of health outcome that reflects the patient’s own judgement. The scores on these five dimensions can be presented as a health profile or can be converted to a single summary index number (utility) reflecting preferability compared to other health profiles.

The EQ VAS records the patient’s self-rated health on a vertical visual analogue scale with 0 representing 'Worst imaginable Health State' and 100 'Best imaginable Health State'.
- PhGA

- The physician's global assessment scale is used for the Investigator to rate the disease activity of their patient using 100 mm VAS ranging from "no disease activity" (0) to "maximal disease activity" (100).

where similar estimand framework as for the primary endpoint described in Section 2.5.1, will be adopted.

All secondary endpoints may be listed by treatment group, subject and visit/time. Descriptive statistics on raw and change from baseline for the continuous data (total scores) as well as for the categorical variables (individual scores of EQ-5D) will be provided by treatment group and visit/time.

Spaghetti plots (except EQ-5D) up to Week 24 will be provided by treatment over time.

### 2.6.2 Statistical hypothesis, model, and method of analysis

The change from baseline for ESSPRI, FACIT-F, EQ VAS and PhGA VAS are assumed to be normally distributed.

A mixed effect model for repeated measurements (MMRM) will be fitted, similar to the primary analysis described in Section 2.5.2, to the changes from baseline for each secondary endpoint, for all post-baseline time points up to (and including) Week 24 visit including the following fixed factors

- treatment group (LOU064 100 mg *qd*, LOU064 100mg *bid*, placebo)
- visit
- treatment group by visit interaction
- stratification factor baseline ESSDAI score  $<10$  or  $\geq 10$

and baseline corresponding secondary endpoint fitted, as a continuous covariate. An unstructured variance-covariance matrix will be fitted to model the dependency between repeated observations. Graphical checks on the model assumptions of normality of the data will be provided.

Both unadjusted and adjusted mean values of change from baseline will be presented along with standard error. The difference in the mean change from baseline of each secondary endpoint, at each visit between LOU064 (*qd* and *bid* averaged) and placebo will be estimated from the model and presented together with the associated 95% confidence intervals and one-sided p-value. In addition, the difference in the mean change from baseline of each secondary endpoint, at each visit between LOU064 dosing regimens (*qd* vs *bid*) will be presented along with the associated 95% confidence intervals.

### 2.6.3 Handling of missing values not related to intercurrent event

Missing data will not be imputed. If missing data occurs in a domain, the corresponding total measurement will be set to missing. If a baseline assessment is missing (and there is no screening value available to replace it), the corresponding change from baseline value will be missing.

The MMRM utilized for the analysis implicitly imputes missing data under a missing at random assumption.

#### **2.6.4 Supplementary analyses**

Commercially Confidential Information

### **2.7 Analysis supporting exploratory objectives**

The FAS analysis set will be used for the analysis described here.

#### **2.7.1 Exploratory endpoint(s)**

Commercially Confidential Information

#### **2.7.2 Statistical hypothesis, model and method of analysis.**

Commercially Confidential Information

Commercially Confidential Information

## **2.8 Safety analyses**

All subjects within the SAF analysis set will be included for the safety analyses.

### **2.8.1 Adverse events (AEs)**

All information obtained on adverse events will be displayed by treatment group and subject.

The treatment emergent adverse events (TEAEs) will be summarized by treatment group, primary system organ class, preferred term and by maximum severity (separately). A subject with multiple adverse events within a body system is only counted once towards the total of this body system. TEAEs will be also summarized by preferred term suspected to be related to treatment.

Serious TEAEs will be also summarized by treatment group preferred term and causality.

Graphical methods (such as bar plots) will be used to present the infections by severity and treatment groups and the number of subjects with infections by severity and treatment groups.

Commercially Confidential Information

## Commercially Confidential Information

**2.8.1.1 Adverse events of special interest / grouping of AEs**

The number (and proportion) of subjects with AEs of special Interest (AESI) will be summarized by treatment group and risk level. List of AESI can be found in Appendix 5.2.1.

**2.8.2 Deaths**

All information obtained on deaths will be displayed by treatment group and subject.

Separate summary statistics will be provided for deaths, serious adverse events and other significant AEs leading to discontinuation, by treatment group.

**2.8.3 Laboratory data**

Laboratory data with any abnormal values will be listed by treatment group and subject; in case of any value outside the normal range in a parameter in a subject, all records of this parameter will be presented. Summary statistics will be provided by treatment and visit/time.

The number and percentage of subjects with newly occurring clinically notable post-baseline laboratory results will be presented for all assessments performed. Clinically notable laboratory values can be found in Appendix 5.3.

Newly occurring liver enzyme abnormalities will be tabulated by treatment and timepoint.

Spaghetti plots will be provided by treatment group and visit/time.

**2.8.4 Other safety data****2.8.4.1 ECG and cardiac imaging data**

Triplicate measurements on ECG are scheduled for some visits. For numeric measurements, the mean of the triplicate measurements will be used.

PR, QRS, QT, QTcF, and RR intervals will be obtained from 12-lead ECGs for each subject during the study. ECG values with any abnormal values will be listed by treatment group and subject.

Summary statistics will be provided by visit/time by treatment group. In addition the number and percentage of subjects with clinically notable post-baseline ECG abnormalities on QT and QTcF intervals and with noteworthy PR, QRS and Heart Rate interval or changes from baseline will be presented. Details in regards to notable intervals can be found in Appendix 5.3.

Spaghetti plots will be provided by treatment group and visit/time.

**2.8.4.2 Vital signs**

Vital signs values outside normal range will be listed by treatment group and subject.

Summary statistics will be provided by visit/time by treatment group. The number and percentage of subjects with clinically notable post-baseline vital signs will be presented. Details in regards to notable intervals can be found in Appendix 5.3.

Spaghetti plots will be provided by treatment group and visit/time.

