12.5.2 Safety endpoints

All safety endpoints (i.e. AEs, laboratory data, vital signs, and ECG) will be summarized by treatment for all subjects in the safety set.

Adverse events

All information obtained on AEs will be displayed by treatment group and subject.

The number (and percentage) of subjects with treatment emergent AEs (events started after the first dose of study medication or events present prior to start of double-blind treatment but increased in severity based on preferred term) will be summarized in the following ways:

- by treatment, primary system organ class and preferred term.
- by treatment, primary system organ class, preferred term and maximum severity.
- by treatment, Standardized MedDRA Query (SMQ) and preferred term.

Separate summaries will be provided for study medication related AEs, deaths, serious adverse events, and other significant AEs leading to discontinuation. A subject with multiple AEs within a primary system organ class is only counted once towards the total of the primary system organ class.

Laboratory data

The summary of laboratory evaluations will be presented for four groups of laboratory tests (hematology, serum chemistry, urinalysis and coagulation). Descriptive summary statistics for the change from baseline to each study visit will be presented. These descriptive summaries will be presented by test group, laboratory test and treatment group. Change from baseline will only be summarized for subjects with both baseline and post baseline values.

Vital signs

Analysis of the vital sign measurements using summary statistics for the change from baseline for each post-baseline visit will be performed. These descriptive summaries will be presented by vital sign, treatment group and visit/time. Change from baseline will only be summarized for subjects with both baseline and post-baseline values. Shifts with respect to normal ranges and number and percentage of notable abnormalities will also be summarized.

ECG

Summary statistics will be provided by treatment and visit/time.

PR, QRS, QT, QTcF, and RR intervals will be obtained from 12-lead ECGs for each subject during the study. Frequency tables will be produced for the number and percentage of subjects with notable QT and QTcF intervals and with noteworthy PR, QRS and Heart Rate interval or changes from baseline.

Commercially Confidential Information

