## 1.2 Study objectives, endpoints and estimands

Objective(s)	Endpoint(s)
Primary objective(s)	Endpoint(s) for primary objective(s)

 
Commercially Confidential Information
 
	
 
Change from baseline in ESSDAI at Week 24
 

Secondary objective(s)	Endpoint(s) for secondary objective(s)

 
To evaluate the efficacy of LOU064 compared to placebo with respect to change from baseline on patient and physician-reported outcomes over time
 
	
 
Change from baseline in ESSPRI, FACIT-F, EQ-5D and PhGA over time
 

 
Commercially Confidential Information
 
	
 
Change from baseline in ESSPRI at Week 24
 

 
To evaluate the efficacy of LOU064 compared to placebo with respect to change from baseline in ESSDAI over time
 
	
 
Change from baseline in ESSDAI over time
 

 
To evaluate the safety and tolerability of LOU064
 
	
 
Safety endpoints will include                             
 
Occurrence of treatment emergent adverse events (both serious and non-serious) during the study
 
 
 

Objective(s)	Endpoint(s)

 
To assess PK parameters of LOU064
 
	
 
Occurrence of treatment emergent abnormal vital signs, laboratory and ECG during the study
 
PK parameters AUC, Cmax, Tmax and if feasible MRT and others as needed
 

Exploratory objective(s)	Endpoint(s) for exploratory objective(s)

Commercially Confidential Information

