## **4 Change to protocol specified analyses**

No changes from protocol specified analysis were made.

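### SAP 2.8.4.2 counts notable vital signs after baseline without a baseline condition and omits the protocol's shift summary, so the treatment-emergent endpoint is not tabulated as stated

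*SAP*

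**What the plan says.** Protocol Table 2-1 and SAP 1.2 give the same secondary safety endpoint: "Occurrence of treatment emergent abnormal vital signs, laboratory and ECG during the study". The SAP then treats the three data types differently.

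- **Laboratory (SAP 2.8.3):** "The number and percentage of subjects with newly occurring clinically notable post-baseline laboratory results will be presented".
- **ECG (SAP 2.8.4.1):** "the number and percentage of subjects with clinically notable post-baseline ECG abnormalities on QT and QTcF intervals", and in the same sentence "noteworthy PR, QRS and Heart Rate interval or changes from baseline will be presented".
- **Vital signs (SAP 2.8.4.2):** "The number and percentage of subjects with clinically notable post-baseline vital signs will be presented". The section also has a listing of out-of-range values, summary statistics by visit, and spaghetti plots.

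For vital signs, protocol 12.5.2 asks for more: "Shifts with respect to normal ranges and number and percentage of notable abnormalities will also be summarized". SAP 2.8.4.2 has no shift summary, and its text shows no redaction. SAP Section 4 states: "No changes from protocol specified analysis were made".

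The only definition of treatment-emergent is in SAP 2.1.1, and it covers adverse events: it "refers to any adverse event (AE) started after the first dose of study treatment", or one already present that increases in severity.

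**The concern.** A programmer following SAP 2.8.4.2 would count a subject with a systolic pressure of 145 mmHg at baseline and 143 mmHg at Week 4. That value is notable and post-baseline, but it did not emerge on treatment. The limits in protocol 16.1 are absolute and commonly crossed: systolic below 90 or at least 140 mmHg, diastolic below 60 or at least 90 mmHg, heart rate below 50 or above 100 bpm. No blood pressure limit appears among the readable entry criteria.

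The resulting percentage would mix pre-existing high or low pressure with on-treatment change. It would overstate incidence in every arm and compress the contrast between arms. With about 24 subjects per arm, chance differences in baseline blood pressure would also enter the comparison. The shift summary is the output that would separate the two components, and it is the one missing.

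**Working it through.** The documents give no rate or power for this endpoint, so there is no stated figure to reproduce. The first step compares text; the rest is illustration.

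**1. Text.** SAP 2.8.3 and 2.8.4.2 both send the reader to Appendix 5.3 for what counts as notable. Section 2.8.3 nevertheless puts its new-onset condition in its own sentence, and 2.8.4.2 has none. The natural reading is that 2.8.4.2 sets no baseline condition. Separately, protocol 12.5.2 lists two vital-sign items, shifts and notable counts. SAP 2.8.4.2 carries only the second.

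**2. Would a baseline-notable subject be counted again?** Table 8-1 gives 8 post-baseline vital-sign visits (Weeks 2, 4, 8, 12, 16, 20, 24 and EOS). If such a subject is notable at each visit with probability r, and visits are taken as independent (an assumption), the chance of being counted is 1 − (1 − r)^8:

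- r = 0.3: 1 − 0.7^8 = 94.2%
- r = 0.5: 1 − 0.5^8 = 99.6%
- r = 0.7: 1 − 0.3^8 = 99.99%

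**3. Effect on the contrast.** Let b be the share notable at baseline, all taken as counted, and q the new-onset rate among the rest. The planned rate is b + (1 − b)q, so the between-arm difference is (1 − b)(q_drug − q_placebo). Assume q = 10% on placebo and 25% on LOU064, which gives a new-onset ratio of 2.50 and a difference of 15 points.

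| b (assumed) | Placebo | LOU064 | Difference | Ratio |
|---|---|---|---|---|
| 10% | 0.10 + 0.90 × 0.10 = 19.0% | 0.10 + 0.90 × 0.25 = 32.5% | 13.5 points | 1.71 |
| 20% | 0.20 + 0.80 × 0.10 = 28.0% | 0.20 + 0.80 × 0.25 = 40.0% | 12.0 points | 1.43 |
| 40% | 0.40 + 0.60 × 0.10 = 46.0% | 0.40 + 0.60 × 0.25 = 55.0% | 9.0 points | 1.20 |

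At b = 20%, 24 × 0.28 = 6.7 placebo subjects would be counted, of whom 24 × 0.80 × 0.10 = 1.9 are new.

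**4. Chance imbalance.** For 24 placebo and 48 LOU064 subjects, the SD of the difference in baseline-notable share is √[b(1 − b)(1/24 + 1/48)]. At b = 20% this is √(0.16 × 0.0625) = 10 points. Most of any such imbalance passes into the planned count.

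**5. Simulated systolic pressure.** Step 3 takes every baseline-notable subject as counted. A simulation relaxes that: subject mean plus visit error, 8 post-baseline visits, threshold 140 mmHg, and a +5 mmHg drug shift. All parameters are assumed. The share notable at baseline is 1 − Φ[(140 − mean)/√(between SD² + within SD²)].

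| Mean, between SD, within SD | b | Counted again (no drug effect) | Difference as planned | Difference, new onset only |
|---|---|---|---|---|
| 120, 12, 8 | 1 − Φ(20/14.42) = 8.3% | 86% | 13.7 points | 14.1 points |
| 125, 14, 8 | 1 − Φ(15/16.12) = 17.6% | 93% | 13.4 points | 15.2 points |
| 130, 15, 9 | 1 − Φ(10/17.49) = 28.4% | 95% | 11.7 points | 15.1 points |

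The relative loss is 1 − 13.7/14.1 = 3%, 1 − 13.4/15.2 = 12% and 1 − 11.7/15.1 = 23%, somewhat below b in each case. The (1 − b) rule is therefore close to an upper bound on the dilution in these scenarios.

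**The case against.** **The text is silent, not explicit.** SAP 2.8.4.2 never says that baseline-notable subjects are counted. Appendix 5.3 is redacted and could hold a baseline rule, and several exclusion criteria are redacted and could hold a blood pressure limit. This stands as a limit on certainty. The contrast with 2.8.3 makes the plain reading likely but does not prove it.

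**The count follows the protocol.** A reader might infer that SAP Section 4 is wrong about the count as well. The documents do not support that. Protocol 12.5.2 asks for notable abnormalities without a new-onset condition, and protocol 16.1 likewise speaks only of notable values and change from baseline. Section 4 is contradicted by the missing shift summary alone.

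**ECG.** A reader might extend the criticism equally to SAP 2.8.4.1. It is much weaker there. Screening excludes QTcF of at least 450 ms (male) or 460 ms (female) and ECG heart rate below 50 bpm, against notable QTcF limits of above 450 and 460 ms. Changes from baseline are also mentioned in that section.

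**Practical size.** A reader might infer that a real signal would be hidden. The calculations do not show that. In the simulated scenarios the expected z for 24 versus 48 subjects moves only from 1.21 to 1.27, 1.08 to 1.17 and 0.97 to 1.04 on restriction to new onset. Protocol 12.5.2 also specifies change from baseline at each visit, and the SAP's listings and plots show individual values. This stands: the fault is mainly that the table does not report the stated endpoint.

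**A new-onset count alone has a gap.** It would miss a subject who goes from 145 to 180 mmHg, although the SAP's adverse-event definition includes worsening. This also stands, and it is a reason to restore the shift summary alongside the count.

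**Conclusion.** The point holds for vital signs, and in practice mainly for blood pressure. On the readable text, the planned count ignores baseline status and so does not deliver the treatment-emergent endpoint named in both documents. It is also inconsistent with SAP 2.8.3. The absence of the protocol's shift summary, with no change declared in Section 4, needs no assumption beyond the published text.

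The consequence is confined to descriptive safety tables; the primary analysis is untouched. Its size depends on the share of subjects notable at baseline, which the documents do not give. The between-arm difference shrinks by roughly that share, and by less if some of those subjects are never counted again. The conclusion also assumes that the redacted appendix and exclusion criteria contain neither a baseline rule nor a blood pressure entry limit.

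**What to change.** - In SAP 2.8.4.2, count subjects with *newly occurring* notable vital signs. For each criterion, use as denominator the subjects not notable on that criterion at baseline, and show that number.
- Restore the protocol's vital-sign shift summary, as baseline category by worst post-baseline category, so that worsening from an already notable baseline stays visible. If it is being dropped on purpose, say so in SAP Section 4.
- If Appendix 5.3 already holds a baseline rule, state it in the text of 2.8.4.2.
- Using the same wording in SAP 2.8.4.1 is a minor consistency edit.

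The cost is SAP wording, one changed table shell and the shift output the protocol already calls for. All data are collected already. The downside is smaller denominators: at an assumed 20% notable at baseline, 24 × 0.80 = 19.2 placebo and 48 × 0.80 = 38.4 LOU064 subjects for that criterion.
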